**Procedures performed for research purposes only:**

Survey Questionnaires will be given to all patients who qualify for, and are being scheduled by their treating physician for, peripheral nerve stimulator placement and are willing to enter. Within the survey questionnaire, pre-procedure and post-procedure NRS pain scores for both back and leg will be obtained for research purposes. Also, current pain medications of patients throughout treatment will be obtained for research purposes.

### **Statistical Methods, Data Analysis and Interpretation**

---

Means and standard deviations of subject demographic data, as well as pain, functional, and treatment satisfaction scores will be calculated in addition to survival analysis. Intergroup differences will be assessed by t test for numerical data and Chi Square or Fisher Exact test for categorical data. Regression modeling will be implemented using ANOVA to assess for patient traits and characteristics that increase the likelihood of efficacy using one technique as opposed to the other.

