**Sample Size:**

At Utah:

All Centers: 120

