**Exclusion Criteria:**

1. Refusal to participate, provide consent, or provide follow-up information for the 24-month duration of the study.
2. Contraindications to medial branch targeted PNS (active infection, bleeding disorders, current anticoagulant or antiplatelet medication use, allergy to iodinated contrast, penicillin or clindamycin and pregnancy or breastfeeding).
3. More than 2 levels of clinical proven pain.
4. Active moderate to severe lumbar radiculopathy.
5. Intradural disc herniation.
6. Spinal fracture of posterior elements within the past 6 months.
7. Steroid injection in the spine within the last 30 days.
8. Any intradiscal injection other than contrast dye or anesthetic in the last 30 days.
9. Prior fusion at level considered to be the source of the pain.
10. Prior lumbar spine surgery within the last 6 months.
11. AP diameter of spinal canal less than or equal to 9mm at level to be treated.
12. Severe uncontrolled medical condition.
13. Severe psychological illness.
14. History of Inflammatory arthritis.
15. Malignancy within past 5 years except basal cell or squamous cell skin cancer.
16. Current use of equal to greater than 45mg morphine-equivalent per day of opioid use.
17. A history of alcohol or drug abuse within past 5 years.
18. Use of any investigational drug within past 30 days.

19. Severe anaphylactic/anaphylactoid reaction to any medications used.
20. Pending litigation involving subject's back pain.
21. No insurance coverage for any subsequent tests or procedures.
22. Inability or unwillingness to continue rehabilitation protocols.

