### **Recruitment/Participant Identification Process:**

Our intended subject demographic includes an active population between the ages of 18 and 90 years on the day of enrollment.

**In-PERSON CONTACT:** Participants will be recruited from the practices of the Principle Investigator and the Co-Investigators, the clinics of the University of Utah Orthopaedic Center, University of Utah Farmington Clinic, and the University of Utah South Jordan Health Center, and other University of Utah Hospital and Clinic locations. If the participant appears to be a candidate, he or she will be invited to participate.

**WRITTEN OR ELECTRONIC CHART REVIEW** will also be used to identify potential study participants on the PI and Co-PIs clinical and procedure schedules. The PI, Co-PIs, Clinical Research Coordinator, and Study Coordinator will perform the chart review to determine eligibility.

**REFERRALS:** Additional recruitment from University of Utah Hospitals and Clinics will have flyers posted and information readily available for primary care providers to refer to the PM&R spine clinic. Flyers will be posted in waiting rooms, and clinic bulletin boards.

Participants will be personally invited to participate by either the PI or the Co-PI's in person while in their respective clinics.

Follow up surveys will be made at 1, 2, 3, 6, 9, 12, 24, and 36 months.

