Questionnaires will be administered and collected from the participant through the University of Utah approved survey system of REDCap. PGIC and Patient Satisfaction Score will only be collected on post procedure surveys.

Demographics will be collected in the baseline questionnaire and include the following information:

- 1) Age (years).
- 2) Sex.
- 3) Height (cm).
- 4) Weight (Kg).
- 5) Duration of pain (weeks).
- 6) Radiologic diagnosis based on MRI of the Lumbar Spine.

Following the Standard Treatment Procedure visit, routine scheduled follow-up (surveys) will occur at 1 month (+/- 1 week), 2 months (+/- 2 weeks), 3 months (+/- 2 weeks), 6 months (+/- 2 weeks), 9 months (+/- 2 weeks), 1 year (+/- 2 weeks), 2 years (+/- 2 weeks), 3 years (+/- 2 weeks), at which times all follow-up measures will be obtained. These questions will be administered over the phone or be sent to you using a secure REDCap survey by email. If received by email it will be in the form of two e-mail links in which you will again be asked questions regarding your pain level, changes in activity limitations, symptoms, emotions and

overall quality of life related to your painful condition and to record current use of opioid and non-opioid analgesic use. This part of the survey should take 10 minutes.

The study start date and the outcome assessment timeline will begin at the date of the participant's initial procedure when peripheral nerve stimulator was placed.

This study is intended to monitor outcomes for 3 years following peripheral nerve stimulator placement.

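### The long-term score means will rest on returned surveys, so they describe all enrolled patients only if non-response is unrelated to outcome

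*Combined protocol and SAP*

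**What the plan says.** The whole analysis plan is the short section Statistical Methods, Data Analysis and Interpretation. It states that means and standard deviations of "pain, functional, and treatment satisfaction scores will be calculated", alongside a survival analysis. It adds that "Intergroup differences will be assessed by t test for numerical data", with chi-square or Fisher tests for categorical data and an ANOVA-based regression on patient characteristics. It gives no analysis population, repeated-measures model, missing-data method or sensitivity analysis. The groups to be compared are not defined, and neither are the event and censoring rules of the survival analysis.

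On data collection, Recruitment/Participant Identification Process says "Follow up surveys will be made at 1, 2, 3, 6, 9, 12, 24, and 36 months". Procedures says of the questionnaires: "These questions will be administered over the phone or be sent to you using a secure REDCap survey by email". It also says "This study is intended to monitor outcomes for 3 years following peripheral nerve stimulator placement". No reminder or retention procedure is described, and Informed Consent allows withdrawal at any time.

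The one safeguard on follow-up is item 1 of Exclusion Criteria, which excludes patients who refuse to "provide follow-up information for the 24-month duration of the study". Sample Size gives "All Centers: 120" without a derivation or an allowance for loss.

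**The concern.** A mean needs a score. With no rule for absent scores, a patient who does not answer at month 36 drops out of the month-36 mean. Means at months 3, 12, 24 and 36 may then come from different subsets of patients, and part of any trend between them may reflect who answered rather than how patients fared.

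The late visits are the most exposed: they come last, they are remote, and the final survey lies beyond the 24 months that patients must be willing to complete at entry. They are also the reason for a three-year follow-up. If patients whose pain has returned are the ones who fall silent, the means overstate how long relief lasts. If recovered patients lose interest, they understate it.

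**Working it through.** The plan states no loss rate, effect size, SD or power, so there is no figure of its own to reproduce. The question is how far a returned-survey summary can move under stated assumptions.

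**Inputs from the documents.** N = 120 (Sample Size); eight surveys to 36 months (Recruitment/Participant Identification Process; Procedures).

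**Assumed inputs.** True responder rate p and losses L_R (responders) and L_N (non-responders). The plan defines no responder rate. The value p = 50% is illustrative, near the one-year result of the cohort cited in Background and Introduction.

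**Step 1. Responder rate.**

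- Observed rate = p(1 − L_R) / [p(1 − L_R) + (1 − p)(1 − L_N)]
- Missing counted as non-response = p(1 − L_R)
- 95% half-width = 1.96 × √(0.25/n), with n the number returned

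| L_R / L_N | Overall loss | Returned of 120 | Observed rate | Bias (points) | Half-width (points) | Missing as non-response |
|---|---|---|---|---|---|---|
| 10% / 20% | 15% | 102 | 0.45/0.85 = 52.9% | +2.9 | 9.7 | 45% |
| 15% / 35% | 25% | 90 | 0.425/0.75 = 56.7% | +6.7 | 10.3 | 42.5% |
| 20% / 40% | 30% | 84 | 0.40/0.70 = 57.1% | +7.1 | 10.7 | 40% |
| 20% / 50% | 35% | 78 | 0.40/0.65 = 61.5% | +11.5 | 11.1 | 40% |
| 20% / 20% | 20% | 96 | 0.40/0.80 = 50.0% | 0 | 10.0 | 40% |
| 40% / 20% | 30% | 84 | 0.30/0.70 = 42.9% | −7.1 | 10.7 | 30% |

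With p between 30% and 50%, L_R = 20% and L_N from 30% to 60%, the bias runs from +2.9 to +17.1 points.

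**Step 2. Mean scores.** The plan reports means, so a simulation of 200,000 patients was run on the NRS at the eight visits. Assumed true means were 4.0, 3.2, 3.0, 3.2, 3.5, 3.8, 4.4 and 5.0. Dropout was permanent and more likely at higher pain, with two strengths of dependence. It followed either the last reported score (missing at random) or the current, unreported score (not at random).

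| Dropout depends on | Retained at month 36 | Bias of returned-survey mean, month 36 | Rise from month 3 to 36, true → shown | Bias after regression on earlier scores |
|---|---|---|---|---|
| Last reported pain, weaker | 73% | −0.14 | 1.98 → 1.88 | 0.00 |
| Last reported pain, stronger | 69% | −0.29 | 1.97 → 1.76 | 0.00 |
| Current pain, weaker | 72% | −0.18 | 1.97 → 1.83 | −0.08 |
| Current pain, stronger | 66% | −0.43 | 1.97 → 1.63 | −0.20 |

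The last column uses sequential regression as a stand-in for a mixed model. The loss of effect is understated by between 1 − 1.88/1.98 = 5% and 1 − 1.63/1.97 = 17%. With dropout more likely at lower pain, the bias in the returned-survey mean was +0.16 (last reported) and +0.17 (current). With dropout unrelated to pain it was zero.

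**Step 3. The t tests.** These compare groups, not time points. If loss has the same extent and the same relation to outcome in both groups, the biases in the two means largely cancel. A distortion needs a difference in loss between the groups.

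**Step 4. The survival analysis.** If returning pain leads to silence, those patients are censored informatively. An undefined time-to-event analysis therefore does not repair the means.

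**The case against.** The strongest reply is that the plan is silent rather than wrong. It does not prescribe an analysis visit by visit, or one limited to returned surveys. That is fair: a reader might infer a deliberate complete-case rule, but the text contains none. What stands is the practical consequence, since the named methods offer no other way to treat an absent score.

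Four further inferences are tempting, and the documents do not support them:

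- **That the t tests overstate durability.** They are planned for intergroup differences, not change over time.
- **That loss at month 36 is built in.** The 24-month wording is an inconsistency in an entry criterion, and surveys are scheduled to month 36. Loss is not guarded against, which is a weaker statement.
- **That the bias is favourable.** Nothing in the documents indicates which patients will stop answering.
- **That decline would be hidden.** In the simulation a true rise of about 1.97 points still shows as 1.63 to 1.88.

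It is also true that three of the four upward biases lie inside the confidence half-width for the surveys returned, and that the largest (11.5 against 11.1 points) barely exceeds it. But a confidence interval reflects sampling error only; it does not allow for selective non-response, and more patients would not remove that bias.

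**Conclusion.** The point holds as a conditional one. As written, the long-term means represent all enrolled patients only if non-response is unrelated to outcome, and nothing in the protocol secures or checks that condition. Under the assumed losses (10–20% of responders, 20–50% of non-responders, true rate 50%), a responder rate is overstated by about 3 to 12 points. An NRS mean at month 36 is 0.14 to 0.43 too low under the simulated dropout. Equal loss gives no bias, and the opposite pattern reverses the sign. All these sizes rest on assumed loss rates and pain trajectories, because the documents give neither. The case for a change is that the plan should not depend on an untested condition when a better method costs little. It does not rest on a demonstrated favourable bias.

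**What to change.** Add a paragraph to the statistical section, before long-term data are seen.

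1. **Scores with a baseline** (NRS back and leg, ODI, PROMIS Physical Function and Global 10, PSQ-3, MQS): estimate change at each visit from one mixed model for repeated measures per score. Use all enrolled patients and all returned surveys, with visit as a factor, baseline score, age, sex and pain duration as covariates, and unstructured covariance. Eight visits imply 8 × 9 / 2 = 36 covariance parameters, so name a simpler fallback structure in advance. A patient with no post-procedure survey adds no outcome information to this model, so report how many there are.
2. **PGIC and satisfaction**, which Procedures says are collected only after the procedure: use the same model without an own-score baseline, or with baseline NRS instead.
3. **Sensitivity analysis:** add a delta (tipping-point) analysis for the mean scores. The simulation leaves a bias of −0.08 to −0.20 after modelling when unreported pain drives silence.
4. **Any responder rate:** define it, keep all enrolled patients in the denominator, and show missing counted as non-response as the lower bound.
5. **Reporting:** give response rates and last-known pain by visit.
6. **Consistency:** reconcile the 24-month wording in Exclusion Criteria with the 36-month follow-up.

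The cost is this text, somewhat more analysis work in standard software, and a less favourable lower-bound figure.

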## **Purpose and Objectives**

---

To assess changes in pain, physical function, health-related quality of life, and cost-effectiveness in patients with low back pain, without symptoms of radiculopathy, that have not responded to conservative or traditional interventional measures and are having a SPRINT percutaneous peripheral nerve stimulator placed as standard of care. Patients will be assessed periodically (by questionnaire) after the placement of the SPRINT, FDA approved 60 day, percutaneous peripheral nerve stimulator, targeting the bilateral medial branches at the

suspected level of pain generation. Neither the manufacturer nor the FDA are involved or will have access to data from this study.

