**Inclusion Criteria:**

1. Age greater than or equal to 18 years of age at day of enrollment.
2. Clinical diagnosis of refractory low back pain for >3 months.
3. Magnetic resonance imaging pathology consistent with clinical symptoms/signs at one or two levels.
4. Back pain of at least 4/10 or higher using the Numerical Rating Scale (NRS).
5. Pain duration of more than 12 weeks despite trial of conservative therapy (medications, physical therapy, or chiropractic care) for 2 months.

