**Procedures:**

**Screening Visit:** As participants are identified by the PI or CO-I's as being possible candidates for this study they will be invited to participate. Main inclusion requirement, as listed in inclusion criteria, is that the patient is being scheduled by their treating physician for placement of a peripheral nerve stimulator as standard of care. If patient states interest in the study and wishes to discuss in more detail a research coordinator will call and answer any questions. If patient is interested, and does meet inclusion/exclusion criteria, and does not have time to do the baseline questions at time of appointment a qualified research staff member will call the patient to complete by phone. It is anticipated that most subjects in this study will be identified mainly through the regular flow of the University of Utah clinics. The informed Consent process will occur either at the time the subject is in clinic or the participant may elect to complete the process at a later time. Eligibility is determined by the inclusion and exclusion criteria. Qualifying volunteers will be asked to provide both written and verbal informed consent once a standard of care treatment plan has been agreed upon by the patient and treating physician.

**Baseline:** Participants who meet inclusion and exclusion criteria will be enrolled into the study after consenting to participate and before placement of the peripheral nerve stimulator. Surveys and results will be administered and recorded through REDCap, at the time of collection data will be coded by replacing the participant's name and other identifying information with a study ID number. This interventional procedure is considered standard of care and is typically based on physician preference. Baseline data will be collected within 2

weeks prior to the scheduled procedure, this will include information from their examination and baseline questionnaires which include the following:

1. Physical function (ODI)
2. Analgesic use (MQS III score30)
3. PROMIS Physical Function CAT version 2.0 (PF CAT)
4. PROMIS Global 10
5. Global impression of change (PGIC)
6. The Pain and Sleep Questionnaire (PSQ-3)
7. Numeric Rating Score (NRS) for back and legs
8. Patient Satisfaction Score ( (5 point: 1, very dissatisfied; 2, dissatisfied; 3, neither satisfied nor dissatisfied; 4, satisfied; and 5, very satisfied).

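### The trait analysis names ANOVA but states no baseline adjustment and does not keep numeric traits continuous, so a trait linked to starting pain could look predictive when it is not

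*Combined protocol and SAP*

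**What the plan says.** The whole plan for this analysis is one sentence in Statistical Methods, Data Analysis and Interpretation: "Regression modeling will be implemented using ANOVA to assess for patient traits and characteristics that increase the likelihood of efficacy", which ends "using one technique as opposed to the other". It gives no outcome, time point, covariates or trait coding. Efficacy is not defined as a final score, a change or a responder status.

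Other sections show what is available:
- The baseline questionnaires include "Numeric Rating Score (NRS) for back and legs", together with ODI and PROMIS scores. The section on research-only procedures confirms that "pre-procedure and post-procedure NRS pain scores for both back and leg will be obtained for research purposes".
- Inclusion criterion 4 sets a floor of 4 out of 10 on the NRS, so starting pain can lie anywhere from 4 to 10.
- Age, height, weight and pain duration are recorded as numbers with units. Sex and radiologic diagnosis complete the demographic list.
- The sample size is "All Centers: 120", with no calculation behind it.
- Purpose and Objectives describes patients who "are having a SPRINT percutaneous peripheral nerve stimulator placed as standard of care". No second treatment appears anywhere.

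**The concern.** ANOVA in its ordinary sense compares group means, with no covariate. Used that way here, it raises two problems.

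The first is starting pain. A patient who enters at NRS 4 can lose at most 4 points, and one who enters at 10 can lose 10. Patients who start higher also tend to finish higher. A trait associated with starting pain therefore inherits an apparent association with outcome. The sign depends on the outcome form, which the plan leaves open: the higher-pain group looks worse on follow-up score and better on change. An analyst could reach opposite conclusions from the same data.

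The second is grouping. Numeric traits enter a plain ANOVA only as categories, and cutting a number into groups discards information. With 120 patients there is little to spare.

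**Working it through.** **The plan's own figure.** 120 cannot be reproduced, because no alpha, power, effect size or SD is given. For orientation, at two-sided 5% and 80% power a 60/60 split detects a standardised difference of (1.96 + 0.84) × √(2/60) = 0.51.

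**1. False positives without baseline.** Assumed, because the documents give none of these: 60 v 60 complete patients, baseline SD 1.5 within group, slope of follow-up on baseline 0.5, residual SD 2.2, no direct trait effect.

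- Variance of follow-up score within group: 0.5² × 1.5² + 2.2² = 0.5625 + 4.84 = 5.4025 (SD 2.32).
- Variance of change: (0.5 − 1)² × 1.5² + 2.2² = 5.4025, the same.
- Standard error of a group difference: 2.32 × √(2/60) = 0.424.
- Spurious difference for a baseline gap g: +0.5g on follow-up score (worse) and −0.5g on change (better).
- Rejection rate, normal approximation, with d = 0.5g/0.424: Φ(d − 1.96) + Φ(−d − 1.96).

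| Gap g | d | Rejection rate, scores unbounded |
|---|---|---|
| 0.5 | 0.59 | 9% |
| 1.0 | 1.18 | 22% |

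Bounding the scores moves these figures, as simulation shows. With baseline values outside 4-10 set to the limits, a nominal 1-point gap gives about 20% on each outcome form. If follow-up is also held to 0-10, it gives about 20% on follow-up score (0.44 worse) and 23% on change (0.50 better). If baseline is drawn from a truncated distribution, the realised gap shrinks to 0.77 and the rate is about 14%. Across these choices the range is about 7-10% for 0.5 point and 14-24% for 1 point. With baseline in the model it is about 5% throughout.

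**2. The same check with a numeric trait.** Standardised normal variables, N = 120, trait-baseline correlation ρ, baseline-to-follow-up correlation b, no direct effect, trait kept continuous:

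| ρ | Outcome | b = 0.3 | b = 0.5 | b = 0.7 |
|---|---|---|---|---|
| 0.1 | follow-up score | 6% | 8% | 12% |
| 0.1 | change | 11% | 8% | 7% |
| 0.3 | follow-up score | 16% | 38% | 64% |
| 0.3 | change | 50% | 37% | 25% |

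Baseline-adjusted rates stay between 4.7% and 5.3% for ρ from 0 to 0.4. In step 1, a 1-point gap corresponds to ρ = 0.5/√(2.25 + 0.25) = 0.32. The rates here are higher than in step 1 mainly because this model gives baseline and follow-up equal SDs.

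**3. Precision from adjustment.** Under the step 1 inputs the residual variance falls from 5.4025 to 4.84, a saving of 1 − 4.84/5.4025 = 10% against either follow-up score or change.

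**4. Cost of grouping, if it were done.** For a normal trait with a linear effect, the information kept is the share of the trait's variance that lies between groups:

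| Coding | Share kept | 120 patients act like | Power at r = 0.25 |
|---|---|---|---|
| Continuous | 1 | 120 | 79% |
| Median split | 2/π = 0.637 | 76 | 60% |
| Tertiles | 0.793 | 95 | 59% |
| Quartiles | 0.861 | 103 | 55% |

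Tertile and quartile ANOVA also spend extra degrees of freedom, so their power does not rise with the share kept.

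**The case against.** The strongest reply is that the plan is silent rather than wrong. The sentence speaks of regression modelling, and ANOVA may mean the F tests from a linear model, which accepts both a baseline covariate and continuous predictors. The traits are not listed in that sentence, so baseline scores could be among them. Demographic data are to be summarised by mean and SD, which suggests that they are treated as numbers, and no cut-points appear anywhere. All of this stands. A reader might infer that the plan leaves baseline out or forces numeric traits into categories, but the documents say neither.

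Other strong readings also fail:
- *Any trait linked to starting pain will look predictive.* The inflation depends on the strength of the link. At ρ = 0.1 the rate is only about 6-12%, and the documents give no evidence on how strongly any trait is linked to pain.
- *Much of the information is lost.* That fits a median split (36% lost) better than quartiles (14% lost), and the plan proposes neither.
- *Adjustment saves a third of the variance against change.* The usual formula, (1 + ρ)/2 with ρ the baseline-to-follow-up correlation, needs equal SDs at baseline and follow-up. Here that correlation is 0.5 × 1.5/2.32 = 0.32, so the formula would claim 34%. The saving under the stated inputs is 10%.

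It can also be said that the contrast between two techniques is the more basic fault, since only one treatment is described and adjustment cannot supply a comparator. That is right. But once that wording is removed or defined, the trait model still needs its terms.

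**Conclusion.** The point holds as a gap in specification. The plan names ANOVA, states no baseline adjustment and does not say that numeric traits stay continuous. It therefore permits an analysis with a false-positive rate of about 14-24% for a 1-point baseline gap and 7-10% for 0.5 point, against about 5% when adjusted, with the direction set by the outcome form.

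These sizes rest on assumed gaps, SDs, slope and complete data. The adjusted 5% also assumes that the trait acts on follow-up only through the measured baseline score. The reversal of sign holds whenever the slope lies between 0 and 1. The grouping loss is conditional on grouping being done. The documents do not support saying that baseline is excluded or that categories are required. The contrast between techniques cannot be estimated in a study of one treatment.

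**What to change.** Replace the ANOVA sentence with wording such as:

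> For each trait, the follow-up score at a named time point is regressed on the trait and the baseline value of the same score. Age, BMI (from height and weight) and log pain duration enter as continuous terms; sex and radiologic diagnosis enter as factors. If efficacy is a responder outcome, the same terms are fitted in a logistic model.

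Three decisions go with it:
- Name the scale and time point, since there are several scales and eight follow-up surveys, and define responder status if it is used.
- Global impression of change and satisfaction are collected only after the procedure and have no baseline of their own. Either confine the model to scores that have one, or say which baseline score is used for these two.
- Delete "using one technique as opposed to the other", or define the second technique and how patients come to receive it.

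The cost is a few sentences of text and those decisions. The variables in the model are already collected, so no new data, visits or patients are needed.

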## **Background and Introduction**

---

Low back pain is one of a few conditions which affects all individuals through the lifespan. The etiology of low back pain is multifactorial and in many cases self-limiting, however it also is the leading cause for working age adults to be disabled with more than \$87 billion spent on low back pain disorders in 2013. Listhesis of a vertebral body, chronic compression fractures, lumbar disc herniation, and internal disc disruptions are some primary anatomical abnormalities that can cause back pain and do not have great targeted treatments. that may be more common in these younger age groups reaching 39-42% with a predicted probability above 60% until age 50y. While the natural history of back pain suggests most individuals will return to a prior level of function in 3-6 months, there is a high rate of recurrent episodes which can cause short-term disability. Continued back pain can lead to decreased activity levels and accelerate degenerative changes in the disc and facet joints as described by Kirkaldy-Willis.

Current guidelines for treatment of axial low back pain include a 6-12-week course of conservative care including medications, therapy, acupuncture, chiropractic and exercise before an interventional paradigm of injections and/or surgical treatment. For those individuals who do not improve with conservative care and have predominately axial pain, options are limited as success rates from epidural steroid injections and surgery are 50% or less. Other treatments include chymopapain injection, intradiscal electrothermal annuloplasty (IDET), nucleoplasty, methylene blue injection. All of which have 50% or less likelihood of reducing pain more than 50%, although much of this data is from uncontrolled or prospective case-control studies only.

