## **Design**

---

Prospective Biomedical Intervention or Experiment

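### The trait analysis compares two techniques but only one is described, and in a single treated cohort traits can be reported only as predictors of outcome, not as modifiers of the stimulator's effect

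*Combined protocol and SAP*

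**What the plan says.** The only text on the trait analysis is the last sentence of Statistical Methods, Data Analysis and Interpretation. It plans regression by ANOVA for "patient traits and characteristics that increase the likelihood of efficacy". The sentence does not stop there: the full aim is to find traits that "increase the likelihood of efficacy using one technique as opposed to the other". The same section plans tests of differences between groups. It defines neither the groups nor the techniques, and it does not name the outcome or time point for the trait model.

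Elsewhere the protocol describes one treatment. Under Purpose and Objectives, participants are patients "having a SPRINT percutaneous peripheral nerve stimulator placed as standard of care". The Screening Visit text makes being scheduled for the stimulator the main entry requirement. The section on research-only procedures says who is surveyed: "Survey Questionnaires will be given to all patients who qualify for, and are being scheduled by their treating physician for, peripheral nerve stimulator placement". No untreated group, alternative treatment or allocation is described. The sample size is given as "All Centers: 120", with no derivation.

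**The concern.** A trait modifies efficacy only if the difference in outcome between the treatment and its alternative varies with that trait. The planned sentence asks that kind of question, but the protocol supplies only one side of the comparison.

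The obvious repair is to treat the two-technique phrase as a leftover and delete it. That would leave a search for traits that raise the likelihood of efficacy in an uncontrolled cohort. A trait found that way could be reported as marking the patients in whom the stimulator works better, when the data show only who had better scores afterwards. At stake is what this one analysis may conclude. The descriptive summaries are not affected.

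**Working it through.** The plan has no figure of its own to reproduce here: 120 is stated without an error rate, power, effect size or standard deviation. The check is therefore about what can be estimated.

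**1. The analysis as written.** Let Y be outcome, x a binary trait and T the technique (1 = stimulator, 0 = the other). The model that answers the stated question is

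Y = b0 + b1·x + b2·T + b3·x·T,

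where b1 is the trait's association with outcome under the other technique and b3 is the change in technique effect with the trait. On the documents' description T = 1 for everyone, so

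Y = (b0 + b2) + (b1 + b3)·x.

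Only the two sums can be estimated. The target, b3, cannot.

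**2. The analysis with the phrase deleted.** The trait coefficient is still b1 + b3, with T = 0 now meaning no stimulator. Three assumed scenarios show the consequence. None of these rates comes from the documents.

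| Scenario | Recovery without device (trait / no trait) | Added by device (trait / no trait) | b1 | b3 | Observed response |
|---|---|---|---|---|---|
| A: prognostic only | 40% / 20% | 30 / 30 points | 0.20 | 0 | 70% / 50% |
| B: true modifier | 20% / 20% | 50 / 30 points | 0 | 0.20 | 70% / 50% |
| C: device has no effect | 70% / 50% | 0 / 0 points | 0.20 | 0 | 70% / 50% |

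In each, b1 + b3 = 0.20 and the observed distribution is the same, so any test on this cohort rejects with the same probability. A simulation (5,000 runs per scenario, 60 patients with and 60 without the trait, two-sided 5% chi-square) rejected in 61.5%, 63.3% and 62.1%, equal up to simulation error. The level reflects the assumed rates and is not a prediction for this trial; only the equality matters.

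**3. Could a collected trait behave as in A or C?** Pain duration in weeks is a baseline item. The Background says of back pain in general that "most individuals will return to a prior level of function in 3-6 months". Entry opens just beyond 3 months of pain. A patient enrolled then would be about 4 to 6 months from onset at the 1- to 3-month surveys (3 + 1 to 3 + 3). Shorter duration could therefore go with improvement for reasons unrelated to the device. The documents give no recovery rate for the population enrolled.

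**4. What a comparator would change.** Take scenarios A and B with a hypothetical concurrent untreated group and 30 patients in each of four cells (120 in all). For B the interaction is (0.70 − 0.20) − (0.50 − 0.20) = 0.20, with standard error √[(0.21 + 0.16 + 0.25 + 0.16)/30] = √0.026 = 0.161. The ratio is 0.20/0.161 = 1.24, and power is about P(Z > 1.96 − 1.24) = 24%. Simulation (20,000 runs) gave 25.0% for B and 5.8% for A, where the true interaction is zero. A comparator separates the two cases, though 120 patients would give low power under these rates.

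**The case against.** The strongest reply is that the sentence, read in full, is a between-technique contrast, which is the right kind of comparison for effect modification. On that reading the method is sound and what is missing is the second group. This stands, and it is why the first defect is that the analysis cannot be run. It also limits the second defect. A reader might infer that no correction of the technique wording could help, but if a second technique were defined, recovery common to both would cancel and the remaining problem would be confounding by non-random choice. Only deletion without a comparator leaves the problem in place.

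The natural-history statement is also weak support for any particular size of effect. It concerns return to function rather than pain, covers back pain in general and is followed by a remark on frequent recurrence. The inclusion criteria admit refractory pain of more than 12 weeks, scored at least 4/10, despite conservative therapy. So the documents support saying that shorter duration could predict improvement, not that it should. A calculation of how often duration would be flagged would be ordinary two-sample power under assumed inputs and would not measure a flaw in this plan.

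The consequence should be kept in proportion. The objectives list no predictor aim, and nothing in the documents proposes patient-selection rules. A reader might also take the Design label, "Prospective Biomedical Intervention or Experiment", as encouraging a causal reading. It is a one-line label, and the purpose and procedures sections say plainly that placement is standard of care and that the research procedures are questionnaires. It needs no change on this account.

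**Conclusion.** The point holds in two parts. The between-technique trait analysis cannot be carried out on the study described. If it is reduced to one cohort, an efficacy-modifier conclusion would be unsupported.

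A reader might go further and infer that the conclusion would be wrong. The documents do not show that: it would be right in a case like B and wrong in cases like A and C, and the data could not say which applies. An association reported as predicting outcome after placement would remain a legitimate result.

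The conclusion rests on one premise, that every participant receives the stimulator and no comparator is followed. It does not depend on any assumed recovery rate, standard deviation or group split. It should be corrected before analysis.

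**What to change.** In Statistical Methods, Data Analysis and Interpretation, replace the efficacy and two-technique wording with: *patient traits and characteristics associated with outcome after stimulator placement (prognostic association only)*. Add that these results will not be presented as evidence that a trait changes the stimulator's effect.

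If a second technique was intended, define that group and how its patients are identified, and specify a test of the trait-by-technique interaction. State that technique is not randomised, since the Baseline text says the procedure is usually a matter of physician preference, and check whether 120 patients suffice.

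The first route costs one sentence and a more modest claim, with no new data, visits or patients. The second requires a comparison group that the protocol does not now contain.
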